3. STUDY PROCEDURES

3.1 Study staff

All study procedures will be conducted by UCSF and FDOH research staff. FDOH staff will be responsible for recruiting participants at Magnolia Clinic and Center for Women and Children in Duval County, Florida. The research coordinator or assistants will assess eligibility and consent participants, as well as conduct intervention-related activities. Research staff will track recruitment of participants in site-specific logs each day they recruit.

FDOH will collect and share deidentified data with UCSF (survey data, audio recordings of counseling sessions, and qualitative interviews). UCSF team members will be responsible for data analysis.

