3.2.2 Blinding

Given the nature of the intervention, blinding of participants to which intervention they receive (DST or not) will not be feasible. Clinicians and counselors in the clinic will not be alerted to whether participants used the DST or not; however, participants may discuss information in the DST, unmasking the study arm. Consequently, clinicians and counselors will unlikely be blinded to study interventions. However, at follow-up, study personnel conducting surveys by phone will not be aware of participants’ study arm; assignment will be concealed in a different page of the participant’s record. Consent forms intentionally do not disclose the specific outcome of interest (i.e. PrEP initiation), so as not to influence participant behavior. Additionally, participants will not be aware of their arm assignment until after they have been consented. Study staff will be blinded during quantitative data analysis of participants use of the DST or not. Qualitative data will not be blinded as study participants will be asked about use of the DST.

3.2.3 Baseline procedures (see below changes we will be making to the study procedures based on COVID-19)

Patients

The baseline procedures for patient participants are as follows:

On the day of enrollment:

- Individuals will be handed a laminated information card about the study and eligibility criteria when they present to the front desk for check in. Eligibility criteria on this sheet will include:
 - Identify as a woman
 - Age 18 years old or over
 - Not known to be living with HIV
 - Not known to be taking PrEP
 - English speaking
 - Interested in participating in the study
- If patients self-identify as eligible and interested in learning more about the study, they will be instructed to hold onto the laminated card (indicating to the research assistant that they would like to be approached). If they are not interested in participating, patients will hand this card back to front desk staff.
- Research staff will approach patients who have held onto the card in the clinic waiting room before their appointment and invite them to be screened for study eligibility in a semi-private space. Research staff will share a brief description of the study and assess eligibility using a verbal eligibility checklist.

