- Research staff will give the tablet-based DST to participants randomized to the intervention arm to complete prior to their visit.
- All participants will then have a clinical visit with their healthcare provider, per standard clinic protocol.
 - During the visit, participants who are randomized and consented to audio-recordings will have their visits audio-recorded on a HIPAA-compliant recorder.
- After the clinical visit, each study participant will complete a post-visit survey about their demographics, HIV prevention method choice and experience of the counseling they received. If a participant must leave the clinic without completing her post-visit survey due to time constraints (and not because she wants to withdraw from the study), study staff will attempt to contact the participant using the contact information provided and request that they complete the post-visit survey by phone or email.
 - If the patient does not complete the post-visit survey within 72 hours of their initial visit, study personnel will continue to attempt to have them complete the post 72-hours version of the post-survey (in which the time-sensitive questions pertaining to satisfaction with choice and quality of interpersonal care have been omitted) up to one month after the initial visit.
- Participants will receive a \$20 gift certificate after completion of post-visit survey on the day of enrollment. If a participant does not complete the post-survey on the day of their appointment a \$20 gift certificate will be sent by mail after completing the survey by the RA.
- After completing the post-visit survey, participants who completed an audio-recorded session will receive an additional \$20 gift certificate.
- After the post-visit survey, participants who consented to participate in an in-depth interview will complete the interview in a private room in the clinic immediately following their appointment (in person or via video conference), or schedule the interview with research staff to take place within one week of the visit. After completion of the interview, participants will be compensated with a \$40 gift certificate. Details regarding interview procedures can be found in Section 7.4.
- Study staff will provide each patient with a flyer summarizing the timing of follow-up at three months and providing contact information for study staff in case a participant changes their contact information or wishes to dis-enroll.

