3.2.4 Patient participant follow-up surveys

Each study participant will be contacted by whatever method they prefer (phone, mail, SMS, email, in person at a follow-up medical visit) three months after their study visit to complete a follow-up survey.

The survey will be completed either over the phone with an RA or in the patient's own time, online, using REDCap.

- Patient contact information and enrollment dates will be entered into REDCap at baseline, where follow-up contact due dates will be calculated. RAs will conduct

follow-up attempts via the patient's preferred method, logging each attempt and its outcome in REDCap.

- Participants' study arm assignment will be concealed in a different page of the participant's record, and study personnel will not look up assignment.
- Google Voice will be used for text and phone follow-up contact attempts. By using Google Voice as the platform from which to make calls and send text messages, no personal cell phones will have saved participant information on them. Record of contact with participants will be deleted from the Google Voice account monthly by RAs (i.e. call logs). In the case that we are unable to use Google Voice, we will use study staff landlines to call study participants where no participant information will be saved.
- Contact attempts for the 3 month survey will be declared unsuccessful after 4 weeks.
- \$10 gift certificates for completed surveys will be mailed, or picked up at the FDOH office or clinic if the patient prefers, through coordination with the RAs. For more detail on participant payments, see Section 6.

3.2.5 **Medical record data**

In addition to the above procedures, after participants consent to the study, research staff will obtain participants' medical record numbers (MRN) on the day of their visit. At the conclusion of each day, research assistants will request medical record numbers based on patient names and date of birth on the schedule from clinic staff. Participants who consented to the study will have their medical record number entered into a secure REDCap form that is separate from study survey responses, and links study identification numbers to medical record numbers. Access to this REDcap form will be restricted to FDOH employees, and is password protected on secure servers. RAs will shred the paper copy in the clinic after the MRN entered electronically.

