### 1.6 Study Procedures

Both groups will complete surveys at three measurement timelines: baseline ( $t_0$ ), immediately post-appointment ( $t_1$ ), and at 3-months ( $t_2$ ). Data collection will occur via electronic survey hosted on RedCAP. Neither the participants nor the study team will be blinded.

Research assistants will approach eligible patients in the clinic waiting room prior to their appointments. They will assess eligible and complete consent procedures in private location on site. Participants will then complete a baseline questionnaire on a tablet. After completion of initial questionnaire, participant will be randomized to a treatment using a randomization module in RedCAP. Participants randomized to the intervention group will then immediately receive access to the DST via a tablet provided by the research assistant to review in advance of their clinical visit.

After the participant's visit with the provider, they will be asked to complete a post-visit survey about their clinic visit and counseling, risk perception, decision making, sexual history, and their experience with the decision support tool if they are in the intervention arm.

Three months post-visit, research staff will follow-up with participants by phone, email, or SMS to administer a short survey and ask participants about their chosen HIV prevention method, and if they initiated PrEP.

Upon completion of the study, research staff will extract data from the medical record pertaining to participants' PrEP prescriptions, history of sexually transmitted infections, zip code, and insurance status.

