##### 2.1.2.2 Secondary variables

- **Number of Patients Reporting PrEP use:** Participants will be contacted at follow-up and asked if took PrEP in the past 3 months regardless of where it was obtained.

- **Patient-Perceived HIV risk:** Participants will be asked about how worried they are about getting HIV in the next 6 months.
- **Knowledge of PrEP:** Participants will be asked a series of questions about PrEP to assess PrEP knowledge.
- **Decisional Conflict:** Participants will be asked questions derived from the Decisional Conflict Scale to provide a measure of decision quality about their HIV prevention decision immediately following their visit.
- **Interpersonal Quality of HIV Prevention Care:** A scale for patient-centered HIV prevention counseling focusing on patient preferences and reflecting satisfaction and confidence in the counseling session, derived from the Interpersonal Quality of Family Planning Care Scale developed by the PI.
- **Intention to Use Any HIV Prevention Method:** Participants will be asked if they plan to use any HIV prevention method after the initial visit.
- **Satisfaction with Information Received about HIV Prevention:** Participants will be asked about their satisfaction with HIV prevention counseling.
- Confidence in decision to use an HIV prevention method. A one-time, one-item measure of certainty of plan to use HIV prevention after the initial visit. Participants can select from 4 options: 1 ("completely unsure"), 2 ("mostly unsure"), 3 ("mostly sure, but not 100%"), or 4 ("100% sure").
- **Perceived Quality of Information Received about HIV Prevention:** Participants will also be asked questions about the perceived quality of the HIV prevention information they received during their health care visit.
- **Acceptability of HIV Prevention Methods:** Participants will be asked to rate their preference for a method (even if they never used it). Participants can select from condoms, PrEP, PEP, treatment as prevention, regular partner testing, or other method.
- **Acceptability of the Decision Support Tool:** Participants in the experimental arm are asked four questions about their experiences using the DST.
- Perception of the Decision Support Tool: Participants in the experimental arm will be asked about the degree to which they liked/disliked the tool. Response options vary: "I did not like it at all", "I somewhat disliked it", "I somewhat liked it", "I really liked it".

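### The blinding of phone follow-up staff and of analysts that the protocol states is not secured by the procedures it describes

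*Protocol*

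**What the plan says.** Protocol 3.2.2 makes two claims. At follow-up, "study personnel conducting surveys by phone will not be aware of" the participant's arm; and "Study staff will be blinded during quantitative data analysis of participants use of the DST or not". For the callers, 3.2.4 gives the device: "study arm assignment will be concealed in a different page of the participant's record, and study personnel will not look up assignment". For the analysts, no device is given. Neither document describes coded arm labels or says which survey fields analysts receive.

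On who does what, and what the data contain:

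- Protocol 3.1: "The research coordinator or assistants will assess eligibility and consent participants, as well as conduct intervention-related activities". Protocol 3.2.1 and SAP 1.2 have research staff carry out the randomisation in REDCap.
- Protocol 3.2.3 (baseline procedures): "Research staff will give the tablet-based DST to participants randomized to the intervention arm to complete prior to their visit". SAP 1.6 says that intervention participants "receive access to the DST via a tablet provided by the research assistant".
- Protocol 3.2.4 has RAs make and log the follow-up attempts, and adds: "The survey will be completed either over the phone with an RA or in the patient's own time, online, using REDCap".
- SAP 2.1.2.2, like protocol 7.1.2: "Participants in the experimental arm are asked four questions about their experiences using the DST". Protocol 7.3 places these items in the post-visit survey.

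SAP 1.6 states, contrary to protocol 3.2.2, that neither participants nor the study team are blinded.

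**The concern.** The conflict with SAP 1.6 has to be settled in any case. The point here is what happens if it is settled in the protocol's favour: the trial would then claim two blinds that its procedures do not deliver.

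For callers, the stake is the set of 3-month outcomes that a woman reports to an interviewer: ongoing PrEP use, use of any prevention method, and continuation. An interviewer who knows the arm and works for the trial of the tool can influence how questions are put and how answers are recorded.

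For analysts, the stake is the set of choices the SAP leaves until the data are seen. Blinded analysis is the natural protection for such choices, and a report that claims it should be able to show how it was kept.

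**Working it through.** No figure in the plan bears on this point, so the check sets the sections side by side.

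**1. Can the caller know the arm?**

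- At the visit, research staff randomise the woman and give the tablet to the DST arm only (protocol 3.2.1, 3.2.3). SAP 1.6 names the research assistant as the person who provides it. Whoever does this sees the arm.
- At three months, RAs make the contacts and take the phone surveys (protocol 3.2.4). No separate follow-up team is named.
- No section says that the caller must differ from the person who enrolled or randomised the woman.
- The device in 3.2.4 controls what is read from the record. It does not control what the caller already saw.
- Protocol 3.2.5 shows that the plan can restrict access when it wants to: the form linking study IDs to medical record numbers is limited to FDOH employees and password protected. No such restriction is stated for the allocation page.
- There is a second route. A post-visit survey not done in clinic may be completed later by phone (protocol 3.2.3). The omissions listed for the version used after 72 hours do not include the DST-experience items, so an RA taking that survey can learn the arm from the form.

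**2. Can the analyst know the arm?**

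- The DST-experience items are asked only in the intervention arm (protocol 7.3; SAP 2.1.2.2). A filled item therefore identifies a DST-arm woman. With 192 women planned in that arm out of 384 (SAP 1.2), up to 192 are identifiable directly.
- If the arms were coded A and B, one cross-tabulation of the code against any DST item would show which code is the DST arm, and so unmask both.
- Protocol 8.2 has the survey data exported to Stata and checked for missing values, a step at which this pattern would be visible if the items are in the file.
- The per-protocol analysis (SAP 2) reclassifies intervention women who did not use the tool, so it needs DST-use data as well.
- No section withholds any of this from the analysts.

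**3. Which results are exposed?**

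- H1 is a prescription found in the chart. The IT department extracts it from study IDs and medical record numbers (protocol 3.2.5), and no arm is listed among what it receives. The interviewer problem does not reach it.
- H11-H13 are self-reports compared at three months (SAP 3.3.2). They are exposed when taken by phone.
- H2 concerns reported PrEP initiation. SAP 3.3.2 tests it with H3-H9 right after the visit, while SAP 1.6 asks about initiation at three months. It is exposed to the call only if the 3-month answer is used.
- The open analysis choices are in SAP 3.1 and 3.3.2: collapsing sparse categories, turning strongly skewed scales into binary variables, and choosing a t-test or a sign test.

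**The case against.** The strongest reply is that the documents omit an operational detail and do not describe a failed blind. The same staff category is not the same person, and no roster is given. A woman may answer online with no interviewer. An RA who did enrol her would still have to recall one allocation after three months, among up to 384 women. REDCap logs user actions by user and time (protocol 9.1.2), so the promise not to look has an audit trail behind it. On the analysis side, nothing says that the analyst of H1-H13 receives the DST-only items, and protocol 8.3 has the data for the primary analyses cleaned and locked before those analyses begin. Participants know their arm by design, so self-report bias remains whoever calls.

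Much of this stands, and it rules out the stronger reading. A reader might infer that the blind cannot work. The documents do not show that, because they do not say that the enrolling individual makes the call or that analysts get an unfiltered file. A reader might also try to size the problem as one divided by the number of RAs. That number is not stated, and the ratio would give the chance that caller and enroller coincide, not the chance that the caller knows the arm or the bias that follows.

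What the reply does not do is supply the missing rule. An audit trail cannot address memory. A data lock does not by itself determine which columns the analyst sees. That participants are unblinded is no reason to claim a caller blind without securing it.

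**Conclusion.** The concern holds in limited form: the caller and analyst blinding stated in protocol 3.2.2 and 3.2.4 is not secured as written. It rests on two readings of the text: RAs who deliver the tool are not barred from the calls, and DST-only items are not barred from the analysts' file. If a roster or export specification outside these documents already does both, the remedy is simply to write it in.

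The reach is secondary: interviewer-collected answers for H11-H13, H2 if it is measured at three months, and the scoring choices listed above. A reader might infer that the primary result is compromised. The documents do not support that, since H1 comes from chart extraction without an interviewer. Neither the size nor the direction of any bias can be derived from the documents, because the number of RAs, the share of surveys taken by phone and the content of the analysis file are not given.

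**What to change.** First settle protocol 3.2.2 against SAP 1.6. If the protocol's blinding text is kept:

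- **Callers (protocol 3.2.4).** Require that each phone survey is made by an existing RA who did not enrol or randomise that woman; the same bar should cover an RA who took her post-visit survey by phone. Record the caller's ID. Keep contact by the participant's preferred mode, as 3.2.4 now provides.
- **Access.** Restrict the allocation page and the DST items by REDCap user rights. This is a supporting measure only: RAs who call some women may randomise others, so the different-caller rule does the main work.
- **Analysts (protocol 3.2.2, with a matching line in the SAP).** Supply a coded-arm file without the DST-only items (H14-H18) and DST-use data. Release those, and run the per-protocol analysis, only after the H1-H13 scoring decisions and code are locked.

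If the SAP's text is kept instead, withdraw the blinding statements in 3.2.2 and 3.2.4 and report open conduct.

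The cost is protocol and SAP wording, access settings, a somewhat less flexible call roster and a split data export. The caller rule needs at least two RAs; the protocol refers to them in the plural but gives no number. Sample size and outcomes do not change.

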3.2.6 Participant disenrollment procedures

Participants who express the desire to discontinue their participation in the study will be withdrawn from the study.

Electronic data for participants who dis-enroll at any point

1. Mark participant as "dis-enrolled" in backend survey of REDCap.
2. Remove from follow-up calendar in REDCap.
3. Delete all contact information from REDCap.
4. Mark participant as "dis-enrolled" in tracking docs.

Paperwork

If a participant disenrolls at baseline and a paper consent form had been used, research assistants will move any study participant paper consents and/or HIPAA forms to the folder labeled "withdrawn patients," stratified by clinic. Research assistants will mark on any remaining paperwork the step at which the participant was when they disenrolled, e.g. mark on consent that the participant disenrolled before completing the HIPAA form.

If a participant disenrolls at any point after baseline (e.g. at 3 month follow-up) and had filled out a paper consent form at baseline, their consent and HIPAA forms will remain in the folder with the rest of the remaining enrolled participants. The procedure for electronic records will then be followed.

4. ELIGIBILITY

4.1 Patient eligibility

We are seeking to recruit female participants presenting to two reproductive health clinics in Duval County, Florida (Magnolia and Center for Women and Children).

Inclusion and exclusion criteria are the same at all study sites.

Inclusion Criteria:

- Self-identify as a woman (regardless of pregnancy status)
- Age 18 years old or over
- Not known to be living with HIV (based on self-report)
- English speaking

- Interested in participating in the study

Exclusion criteria:

- Unable to consent
- Currently using PrEP
- Cisgender men
- Unwilling to be contacted in 3 months
- Already participated in the study

4.2 Provider / counselor eligibility for audio-taped counseling visits

We are seeking to recruit providers from two reproductive health clinics in Duval County, Florida (Magnolia and Center for Women and Children).

Inclusion Criteria:

- Providing health care services, including family planning counseling, in one of the participating clinics (includes MDs, DOs, nurse practitioners, physician assistants, nurses, and health educators)

5. PARTICIPANT RECRUITMENT

Patient

Recruitment of study participants will be conducted by FDOH study coordinator and research assistants based on coordination with clinic directors and staff at each study site. Procedures will be tailored to meet the needs of clinic flow at each site.

Each clinic will identify a point person, likely at the front desk, who will hand a laminated information card about the study and eligibility criteria to patients when they present to the front desk for check in. If patients self-identify as eligible and are interested in participating, they will hold onto the laminated card (indicating to the research assistant that they would like to be approached). If they are not interested in participating, patients hand this sheet back to front desk staff.

Study staff will approach potential participants in the waiting room and invite them to a semi-private room where they will share a brief description of the study and assess eligibility using a verbal eligibility checklist. All recruitment, consent, and baseline activities may occur before, during or after appointments in accordance with clinic flow.

If the patient is eligible and wishes to participate, the research assistant will complete the consent process and enroll her in the study.

Providers

At the invitation of the clinics, research staff will attend provider and staff meetings. The intervention will be discussed, study procedures will be explained, and questions will be answered. Providers and counselors will also be invited to meet individually with study staff to answer questions about the study, and audio recording of clinic visits of participants who consent.

